7.6.1.2 Freedom from MBS at 2 Hours Post-Dose

Freedom from each subject's MBS is assessed using the number of mITT subjects who report that their MBS (reported at migraine onset) is absent at 2 hours post-dose. The symptoms that can be nominated as the MBS (phonophobia, photophobia or nausea) are measured using a binary scale (0=absent, 1=present). The information of MBS is directly summarized as follows:

A table showing descriptive statistics for the observed data, which includes the number and percentage of subjects reporting MBS present, MBS absent, MBS not reported and each of the migraine associated symptoms (phonophobia, photophobia or nausea) at baseline and

each post-dose timepoint by treatment group and overall. The table will include exact (Clopper-Pearson) 95% CIs for each percentage of MBS present/absent/not reported.

The difference in percentage of MBS free subjects (“risk difference”) between treatment groups, is evaluated by computing the common risk difference, using CMH weights (sample size weights), stratified by the use of prophylactic migraine medication (yes or no) and country (China or Korea). The risk difference will be tested at a two-sided alpha level of 0.05. Missing data at 2 hours post-dose will be imputed as failure (NC=F). Also, the use of rescue medication prior to providing data at the 2 hour assessment, taking IP prior to reporting the MBS, or failure to report a MBS are events that are imputed as treatment failures. If a stratum (prophylactic medication use: yes or no) has sparse data (less than 5 subjects) then the strata will be pooled.

Sensitivity analyses will be conducted as follows:

1. The primary analysis is repeated, using the mITT population, with missing data at 2 hours post-dose imputed using LOCF. BOCF is permitted.
2. The primary analysis is repeated, using only data from complete cases (data present at baseline and 2 hours).

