After randomization, the subject will be dispensed a single dose of the double-blind study medication that will be taken at the time a migraine attack reaches moderate or severe pain intensity (described below) on the numeric rating scale (NRS) as indicated in the electronic diary (eDiary). The subject will be instructed to take their study medication, as an outpatient, when (if) they have a migraine headache which reaches moderate or severe pain intensity and only after they have identified their most bothersome migraine-associated symptom (phonophobia, photophobia or nausea) in the eDiary. The subject will complete an eDiary for forty-eight hours after taking study medication. The subject will telephone the study center immediately if a severe or serious adverse event occurs.

Subjects will record efficacy data in their eDiary. This includes the following: onset time of headache, intensity of the headache prior to *and* at time of taking study medication. Subject should not dose with study medication until headache reaches moderate to severe intensity. Headache severity will be recorded using a four-point numeric rating scale (no pain, mild pain, moderate pain, severe pain) at the onset of the migraine and after dosing at time points of 15, 30, 45, 60, and 90 minutes and 2, 3, 4, 6, 8, 24 and 48 hours. The presence or absence of associated symptoms (nausea, photophobia, phonophobia) and ratings of functional disability (four-point scale: normal, mildly impaired, severely impaired, requires bedrest) will be recorded at the same time points as the headache severity ratings. Subjects who experience reduction of headache pain to a mild intensity or pain free intensity level will be considered to have achieved pain relief. The subject who does not experience relief of their migraine headache at the end of two hours after dosing with study medication (and after the two hour assessments have been

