| Procedure | Screening Visit (3-28 days) ¹ | Baseline Visit (Randomization) ¹ | Onset of moderate or severe migraine ² | During Treatment 15, 30, 45, 60 and 90 minutes Post-Dose | During Treatment 2, 3, 4, 6, 8 hours Post- Dose | During Treatment 24 hours Post-Dose | During Treatment 48 hours Post- Dose | End of Treatment Visit (within 7 days of migraine) ¹⁴ |
|---|--|--|---|--|---|-------------------------------------|--------------------------------------|--|
| Efficacy Assessments ¹¹ | | | | | | | | |
| Assessment of migraine pain ¹² | | | × | X | × | × | × | |
| Assessment of Migraine Symptoms | | | × | × | × | × | × | |
| (photophobia, phonophobia, and nausea - eDiary) ¹² | | | | | | | | |
| Functional Disability Scale ¹² | | | × | × | × | × | × | |

¹ Screening Phase will be 3 - 28 days. The Baseline Visit may be scheduled but should only occur after all screening procedures are complete, subject meets inclusion/exclusion criteria, and lab test results have been received by the site. ² Subjects will use eDiary to answer questions about their migraine symptoms upon experiencing a moderate/severe migraine headache. The subject will administer pre-dispensed study drug if 1) the headache remains moderate or severe; 2) the subject has completed all required migraine assessment questions in the eDiary, including their current most bothersome migraine symptom, and 3) the subject has not already taken prohibited medications (see protocol section 5.4).

³ Subjects should keep track of their concomitant medications throughout the study and report them to the study personnel at the End of Treatment Visit. Any medication taken for recurrent headache should be documented. Use of concomitant medications after randomization, including rescue medications, will be recorded by the subject on a paper diary and reported to the site. 4 Height will only be captured at the Screening Visit. Weight, body temperature, respiratory rate, blood pressure and heart rate will be collected at all time points where indicated. Sitting arterial systolic and diastolic blood pressure and pulse rate will be measured.

⁵ Screening Visit: All screening visit laboratory test results must be received prior to Baseline (randomization) Visit.

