6.3.2 Nausea, Phonophobia and Photophobia

The migraine associated symptoms of photophobia, phonophobia and nausea are measured on a two point scale (present or absent), using the eDiary, at the time points listed in Table 1. If a subject reports the presence of a symptom, the subject is then asked to rate the severity of the symptom on a four point scale (none, mild, moderate or serve). All assessments are done using the eDiary.

The subjects are also asked to identify their most bothersome symptom on the eDiary (nausea, phonophobia or photophobia) at the onset of the migraine to be treated. The most bothersome symptom must be identified before the subject takes study medication.

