7.6.4 Exploratory Efficacy Analyses

7.6.4.1 Binary Exploratory Endpoints

The binary exploratory endpoints will be evaluated using the same methodology described in section 7.6.1.1. The definitions of the binary exploratory endpoints are listed in the table 1 below.

Table 1 Definitions of the Binary Exploratory Endpoints

| Endpoints | Definition of Success | Missing Data or Rescue Medication Handling |
|---|--|--|
| Pain Relief at 15, 30, 45, 60, and 90 minutes, 3, 4, 6, 8, 24, and 48 hours post-dose | Report a pain level of none or mild (responses of 0 or 1 on the 4-point Likert scale) at specified post-dose time point | NC=F; RM=F |
| Pain freedom at 3, 4, 6, 8, 24, and 48 hours post-dose | Report a pain level of none (responses of 0 on the 4-point Likert scale) at specified post-dose time point | NC=F; RM=F |
| Freedom from MBS at 3, 4, 6, 8, 24, and 48 hours post-dose | Report an absence of their MBS (reported at migraine onset) at specified post-dose time point | NC=F; RM=F; IP=F |
| Function normally at all post-dose timepoints except 2 hours | Subjects who report “abnormal” at baseline and have a response of “normal” at specified post-dose time point | NC=F; RM=F |
| Freedom from phonophobia at all post-dose time points | Subject who have phonophobia present at baseline and have absence of phonophobia at specified post-dose time point | NC=F; RM=F |
| Freedom from photophobia at all post-dose time points | Subject who have photophobia present at baseline and have absence of photophobia at specified post-dose time point | NC=F; RM=F |
| Freedom from nausea at all post-dose time points | Subjects who have nausea present at baseline and have absence of nausea at specified post-dose time point | NC=F; RM=F |
| Sustained pain relief from 2 to 24 hours | Subjects that experience no or mild headache pain (response of 0 or 1 on Likert scale) at all time points from 2 through 24 hours post-dose; Subjects with missing pain scores at 1 or fewer | NC1=F; RM=F |

| Endpoints | Definition of Success | Missing Data or Rescue Medication Handling |
|---|---|--|
| | time points, given that they have responses of no or mild pain (response of 0 or 1 on 4-point Likert scale) at all other time points including the 2 and 24 hour post-dose time points, will be considered as successes. | |

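### The MBS co-primary endpoint does not require the nominated symptom to be recorded present before dosing, so an attack without it can count as a response in either arm

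*SAP*

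**What the plan says.** **Nomination is a condition of dosing.** The protocol synopsis (Study Design) lets subjects take study medication "only after they have identified their most bothersome migraine-associated symptom (phonophobia, photophobia or nausea) in the eDiary". Protocol 6.3.2 repeats the rule: "The most bothersome symptom must be identified before the subject takes study medication". Footnote 2 to the schedule of assessments (Protocol 4.3) lists the questions to be completed before dosing, "including their current most bothersome migraine symptom".

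**Presence is a separate item.** Under Protocol 4.3.2.1 and 6.3.2, nausea, photophobia and phonophobia are each recorded as present or absent, at onset and at every post-dose time point.

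**Success and failure.** SAP 7.6.1.2 counts subjects who "report that their MBS (reported at migraine onset) is absent at 2 hours post-dose". Four events count as failure:
- missing 2-hour data: "Missing data at 2 hours post-dose will be imputed as failure (NC=F";
- rescue before the 2-hour report;
- taking study drug before reporting the MBS;
- no MBS reported: "failure to report a MBS are events that are imputed as treatment failures".

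A nominated symptom that was absent before dosing is not on this list.

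**Other endpoints have a starting-state condition.** SAP Table 1 (7.6.4.1) defines freedom from phonophobia as "Subject who have phonophobia present at baseline and have absence of phonophobia at specified post-dose time point", with matching wording for photophobia and nausea. The function endpoint (SAP 4.2.1, 7.6.2.2) requires impairment before dosing.

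**The concern.** The objective is freedom from a symptom of the attack being treated, and a subject who did not have the symptom cannot become free of it. Pain freedom is protected because the mITT definition requires moderate or severe pain at dosing. MBS freedom has no equivalent protection, so it is the only co-primary without a starting-state condition.

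Subjects who respond whatever they were given raise both arms' rates and shrink the difference, on an endpoint that must succeed for the trial to succeed. The outcome of a subject with none of the three symptoms would also depend on how the diary was completed: naming a symptom can give success, while naming none gives failure.

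Neither sensitivity analysis in SAP 7.6.1.2 addresses this. Complete cases keep these subjects. The LOCF analysis permits baseline to be carried forward, so a baseline record of absence could itself become a success.

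**Working it through.** **1. Is there a presence rule anywhere?**

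| Place | Condition that the nominated MBS is present before dosing |
|---|---|
| Dosing conditions (Protocol 4.3 footnote 2, 4.3.2, 7.2.2) | None stated; 'current' or 'currently' most bothersome is asked for in 4.3 and 4.3.2 |
| mITT definition (Protocol 9.3, SAP 6) | None; pain intensity only |
| Endpoint definition (Protocol 3.1, SAP 4.1) | None |
| Primary analysis (SAP 7.6.1.2) | None |
| Time to MBS freedom (SAP 7.6.4.2) | None; all mITT subjects |
| Time to absence of each single symptom (SAP 7.6.4.2) | Yes; restricted to subjects with the symptom at onset |

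**2. Reproduce the plan's power.** Inputs from Protocol Appendix IV: n = 600 per arm, Pearson chi-square, two-sided alpha 0.05, placebo 26%, gain 10 points.

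Power = Φ{ [d − 1.96·√(2·p̄(1−p̄)/n)] / √([p₁(1−p₁) + p₂(1−p₂)]/n) }

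With p₁ = 0.26, p₂ = 0.36 and p̄ = 0.31:
- null term: 1.96 × √(2 × 0.2139/600) = 0.0523;
- denominator: √((0.1924 + 0.2304)/600) = 0.0265;
- power = Φ(0.0477/0.0265) = 96.4%, which matches Table 5 of the appendix.

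**3. Add the affected subjects.** Let f be the share whose nominated MBS is absent before dosing, equal in both arms, and let 95% of them still be symptom-free at 2 hours. Neither figure is in the documents; both are assumptions. The observed rate in each arm is (1 − f)·p + f·0.95, so the gain becomes (1 − f) × 10 points.

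| f | Placebo vs rimegepant | Gain (points) | Power as written | Power if scored as failure | Power if excluded (n per arm) |
|---|---|---|---|---|---|
| 0% | 26.0% vs 36.0% | 10.0 | 96.4% | 96.4% | 96.4% (600) |
| 2% | 27.4% vs 37.2% | 9.8 | 95.35% | 95.91% | 96.06% (588) |
| 5% | 29.5% vs 39.0% | 9.5 | 93.53% | 95.14% | 95.55% (570) |
| 10% | 32.9% vs 41.9% | 9.0 | 89.75% | 93.62% | 94.55% (540) |

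The failure column uses rates (1 − f)·p with n = 600. The exclusion column uses the undiluted rates with n = 600·(1 − f). Moving the assumed 95% to 90% or 100% changes the as-written column by less than 0.2 points.

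**4. Joint power.** The appendix multiplies the two powers, assuming independence. With 95% for pain freedom, 0.95 × 0.9353 = 88.9% at f = 5% and 0.95 × 0.8975 = 85.3% at f = 10%, against the stated 90% or so.

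**5. Type I error.** Nomination precedes dosing and is blind. Under the null, the affected share and its outcomes do not depend on arm, so the test keeps its level.

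**The case against.** The strongest reply is that the protocol asks for the symptom that is currently most bothersome, after questions about current pain and symptoms, and separates this from the typical MBS recorded at screening. In plain reading such a symptom is present. The eDiary may also refuse nomination of a symptom marked absent; its branching is not described. This stands as a reason to think the affected share may be small. It does not supply a rule, because the analysis text would still score such a subject as a success.

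A reader might infer more than the documents support:
- **That success is automatic.** It is not. Missing 2-hour data, rescue before the 2-hour report, or the symptom appearing by 2 hours all give failure.
- **That a symptom-free subject is forced to name something.** This depends on eDiary logic that is not shown.
- **That the SAP expects absent MBS at baseline because its descriptive table has such a row.** The same rows serve every time point, so this may be only layout.
- **That power is certainly below 95%.** The share is unknown, and at 2% the result is about 95.4%. The planning rates come from three earlier trials. If those scored MBS the same way, the dilution is already in the 26% and 36%, and the table above counts it twice.

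The contrast with single-symptom endpoints is also softer than it looks. They need a presence condition because not every subject has each symptom, whereas the MBS is chosen by the subject. Finally, scoring affected subjects as failures shrinks the gain by the same factor, to 9.0 points at 10%. It recovers power only because the rates are lower. Excluding them keeps the 10 points.

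**Conclusion.** The gap in the definition is real: as written, SAP 7.6.1.2 can count a subject who never had the nominated symptom as a responder. The consequence is non-differential dilution, not bias in favour of rimegepant, and type I error is unaffected.

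The power loss is conditional. For 26% vs 36% with 600 per arm it is about 1, 3 or 6.6 points at assumed shares of 2%, 5% or 10%. This rests on an equal share in both arms, on 95% of affected subjects staying symptom-free, and on planning rates that do not already contain the effect. The documents establish neither the share nor the last condition. The case for changing the text therefore rests mainly on the definition of a co-primary endpoint, with power as a secondary reason.

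**What to change.** Before unblinding:

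1. In SAP 4.1 and 7.6.1.2, require the nominated MBS to be recorded present at the last pre-dose assessment, and absent at 2 hours, for a subject to count as a success. If the eDiary already enforces presence at nomination, one sentence saying so is enough.
2. Apply the same condition to the other MBS endpoints (SAP 7.6.3.2, the MBS rows of Table 1 in 7.6.4.1, and time to MBS freedom in 7.6.4.2).
3. In the LOCF/BOCF sensitivity analysis, do not let a baseline record of absence be carried forward as a success.
4. Add a sensitivity analysis restricted to subjects with the MBS present before dosing. It keeps the full risk difference.
5. Record the change in SAP 7.10, which now lists none.

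The cost is SAP wording and one extra table, since symptom presence at onset is already collected. If any subjects are affected, MBS-free percentages will be slightly lower in both arms. Results will be less directly comparable with the earlier trials if those scored MBS without this condition.

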7.6.2 Key Secondary Efficacy Analyses

If the co-primary endpoint tests are both significant, then the key secondary endpoints are evaluated using the Hochberg Procedure. See [Section 7.3](#) for details on the procedure.

7.6.2.1 Pain Relief at 2 Hours Post-Dose

Pain relief at 2 hours post-dose is assessed by tabulating the number of mITT subjects that report a pain level of none or mild (responses of 0 or 1 on the 4-point Likert scale) at 2 hours post-dose, by treatment group using the same methodology described in section [7.6.1.1](#).

Subjects with missing data at 2 hours post-dose will be imputed as failures (NC=F). Subjects that use rescue medication prior to reporting pain relief at 2 hours will be classified as failures (RM=F).

7.6.2.2 Function Normally at 2 Hours Post-Dose

Subjects rate the level of disability they perceive as a result of their migraine in performing normal actions using a 4-point scale: Normal Function, Mild Impairment, Severe Impairment, or Required Bedrest. The proportion of mITT subjects who report “abnormal” at baseline and have a response of “normal” at the 2 hours post-dose will be evaluated using the same methodology described in section [7.6.1.1](#).

Subjects with missing data at 2 hours post-dose will be imputed as failures (NC=F). Subjects that use rescue medication prior to reporting function normality at 2 hours will be classified as failures (RM=F).

The information from the 4-point scale will be directly summarized as follows:

A table showing descriptive statistics for the 4-point scale, which includes the number and percentage of subjects reporting each of the 4 disability levels at the specified timepoint post-dose, and the percentage of subjects with missing data, for each treatment group, using the observed data. The table will include exact (Clopper-Pearson) 95% CIs for each percentage.

7.6.2.3 Use of Rescue Medication within 24 Hours

Whether or not a subject took rescue medication within 24 hours after the initial dose of study medication is tabulated by treatment group using mITT subjects, and the percentages are compared between treatment groups using the same methodology described in section [7.6.1.1](#).

Information regarding the rescue medication, including the type, date and time taken, dose, route, and frequency, is presented in a listing by subject and treatment group.

7.6.2.4 Sustained Pain Freedom from 2 to 24 Hours

Sustained pain freedom is assessed using the number of mITT subjects that experienced no headache pain (response of 0 on Likert scale) at all time points from 2 through 24 hours post-dose. Subjects with missing pain scores at 1 or fewer time points, given that they have responses of no pain (response of 0 on 4-point Likert scale) at all other time points including the 2 and 24 hour post-dose time points, will be considered as successes. Subjects with responses missing at greater than 1 post-dose time point, missing data at the 2 or 24 hour time point (i.e. Non-Completers with more than 1 missing data point = Failure; NC1=F), or with any pain score greater than 0; or with any rescue medication within 24 hours (RM=F) will be considered as failures.

The proportion of mITT subjects who have a response of sustained pain freedom from 2 to 24 hours will be evaluated using the same methodology described in section [7.6.1.1](#).

7.6.2.5 Sustained Pain Freedom from 2 to 48 Hours

Sustained pain freedom is assessed using the number of mITT subjects that experienced no headache pain (response of 0 on Likert scale) at all time points from 2 through 48 hours post-dose. Subjects with missing pain scores at no more than 1 time point, given that they have responses of no pain (response of 0 on Likert scale) at the 2, 24, and 48 hour time points will be considered as successes. Subjects with responses missing at greater than 1 time point; missing data at the 2, 24, or 48 hour time point (NC1=F); or with any pain score greater than 0; or with any rescue medication within 48 hours (RM=F) will be considered as failures.

The proportion of mITT subjects who have a response of sustained pain freedom from 2 to 48 hours will be evaluated using the same methodology described in section [7.6.1.1](#).

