Subjects will record efficacy data in their eDiary. This includes the following: onset time of headache, intensity of the headache prior to and at time of taking study medication. Subject should not dose with study medication until headache reaches moderate to severe intensity. Headache severity will be recorded using a four-point numeric rating scale (no pain, mild pain, moderate pain, severe pain) at the onset of the migraine and after dosing at time points of 15, 30, 45, 60, and 90 minutes and 2, 3, 4, 6, 8, 24 and 48 hours. The presence or absence of associated symptoms (nausea, photophobia, phonophobia) and ratings of functional disability (four-point scale: normal, mildly impaired, severely impaired, requires bedrest) will be recorded at the same time points as the headache severity ratings. Subjects who experience reduction of headache pain to a mild intensity or pain free intensity level will be considered to have achieved pain relief. The subject who does not experience relief of their migraine headache at the end of two hours after dosing with study medication (and after the two hour assessments have been completed on the eDiary) will be permitted to use the following rescue medications: aspirin, ibuprofen, acetaminophen up to 1000mg/day (this includes Excedrin Migraine), naprosyn (or any other type of non-steroidal anti-inflammatory (NSAID)), antiemetics (e.g., metoclopramide or promethazine), or baclofen. These are the only medications allowed for rescue treatment after 2 hours post dose of study medication. If at the end of 48-hours after dosing with study medication (but before the End of Treatment Visit) subjects are in need of migraine relief, they may take their prescribed standard of care medications, including triptans if not contraindicated, provided all of the assessments have been completed on the eDiary. Exclusionary rescue medication such as opioids, ergotamines, butalbital compounds, and muscle relaxants (except baclofen as a rescue medication, see above) are not allowed on this study. Similarly, if the migraine is relieved by study medication at 2 hours after dosing but then recurs to a moderate or severe intensity level between two and forty-eight hours, the subject will be permitted to take the same rescue therapy as outlined above. In all circumstances, the subject will always continue to complete his or her eDiary for up to forty-eight hours after consuming the study medication. During the 45 days the subject is participating in the study, if the subject has a nonqualifying migraine (mild migraine) or a migraine that they do not treat with study medication, the subject is permitted to use only the following medications: aspirin, ibuprofen, naprosyn (or any other type of non-steroidal anti-inflammatory (NSAID)), antiemetics (e.g., metoclopramide or promethazine), or baclofen.

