4.2 Secondary Endpoints

4.2.1 Key Secondary Endpoints

1. Pain Relief at 2 hours post-dose, will be assessed using the number of subjects that report a pain level of moderate or severe at baseline and then report a pain level of none or mild at two hours post-dose.
2. The proportion of subjects able to function normally, at 2 hours post-dose, will be assessed using the number of subjects that self-report as “normal” on the FDS in the subset of subjects that report any level of disability just prior to taking study medication.
3. The use of rescue medication will be assessed using the number of subjects that take rescue medication within 24 hours after administration of study medication (rimegepant or placebo).
4. Sustained pain freedom, from 2 to 24 hours, will be assessed using the number of subjects that do not experience any headache pain through the time period of interest.
5. Sustained pain freedom, from 2 to 48 hours, will be assessed using the number of subjects that do not experience any headache pain through the time period of interest.

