| Sustained pain relief from 2 to 48 hours | Subjects that experience no or mild headache pain (response of 0 or 1 on Likert scale) at all time points from 2 through 48 hours post-dose; Subjects with missing pain scores at 1 or fewer time points, given that they have responses of no or mild pain (response of 0 or 1 on 4-point Likert scale) at all other time points including the 2, 24 and 48 hour post-dose time points, will be considered as successes. | NC1=F; RM=F |
| Freedom from MBS from 2 to 24 hours post-dose | Subjects that experience freedom from their MBS at all time points from 2 through 24 hours post-dose; Subjects with missing MBS data at 1 or fewer time points, given that they have responses of freedom from MBS at all other time points including the 2 and 24 hour post-dose time points will be considered as successes. | NC1=F; RM=F; IP=F |
| Freedom from MBS from 2 to 48 hours post-dose | Subjects that experience freedom from their MBS at all time points from 2 through 48 hours post-dose; Subjects with missing MBS data at 1 or fewer time points, given that they have responses of freedom from MBS at all other time points including the 2, 24, and 48 hour post-dose time points will be considered as successes. | NC1=F; RM=F; IP=F |

| Endpoints | Definition of Success | Missing Data or Rescue Medication Handling |
|--|--|--|
| Function normally from 2 to 24 hours post-dose | Subjects that experience normal functioning on the FDS at all time points from 2 through 24 hours post-dose. Subjects with missing FDS scores at 1 or fewer time points, given that they have responses of normal at all other time points including the 2 and 24 hour post-dose time points will be considered as successes. | NC1=F; RM=F |
| Function normally from 2 to 48 hours post-dose | Subjects that experience normal functioning on the FDS at all time points from 2 through 24 hours post-dose. Subjects with missing FDS scores at 1 or fewer time points, given that they have responses of normal at all other time points including the 2, 24 and 48 hours post-dose time points will be considered as successes. | NC1=F; RM=F |

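### The success sentence for sustained pain freedom from 2 to 48 hours (SAP 7.6.2.5) requires no pain only at 2, 24 and 48 hours, and so contradicts the rest of its own definition

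*SAP*

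**What the plan says.** SAP 7.6.2.5 classifies subjects in three sentences.

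- **Opening sentence.** The endpoint counts mITT subjects without headache pain, "response of 0 on Likert scale) at all time points from 2 through 48 hours post-dose".
- **Success sentence.** When at most one score is missing, the condition for success is stated for three assessments only: "response of 0 on Likert scale) at the 2, 24, and 48 hour time points will be considered as successes".
- **Failure sentence.** Failures are subjects with more than one missing score, subjects with a missing score at 2, 24 or 48 hours, "or with any pain score greater than 0; or with any rescue medication within 48 hours (RM=F) will be considered as failures".

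SAP Section 3 schedules pain scores at "15, 30, 45, 60, and 90 minutes and 2, 3, 4, 6, 8, 24 and 48 hours", so seven assessments fall in the 2 to 48 hour window. SAP 4.2.1 describes the endpoint as the number of subjects who "do not experience any headache pain through the time period of interest", and protocol 3.2.1 says the same.

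The parallel success sentences are worded differently. For sustained pain freedom from 2 to 24 hours, SAP 7.6.2.4 requires no pain "at all other time points including the 2 and 24 hour post-dose time points, will be considered as successes". For sustained pain relief from 2 to 48 hours, Table 1 in SAP 7.6.4.1 requires the response "at all other time points including the 2, 24 and 48 hour post-dose time points, will be considered as successes".

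**The concern.** The success sentence limits the no-pain requirement to three of the seven assessments. Pain at 3, 4, 6 or 8 hours does not stop a subject from meeting it, while the failure sentence excludes the same subject. The SAP does not say which sentence takes precedence.

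The endpoint is the fifth key secondary. Under protocol 9.4.2 and 9.4.3 it is tested with the Hochberg procedure once both co-primary endpoints are significant. A responder rule in a confirmatory family should give each subject one label. If the success sentence alone is programmed, a subject whose pain returns at 4 hours and clears by 24 hours counts as a 2 to 48 hour success but a 2 to 24 hour failure. The longer endpoint would then no longer be nested in the shorter one, and its count could even exceed the shorter one's. If this were noticed only after unblinding, the correction would look like a post-hoc choice.

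**Working it through.** **1. One subject, each sentence in turn.** Take scores of 0 at 2, 3, 6, 8, 24 and 48 hours and 1 at 4 hours, with nothing missing and no rescue.

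| Text | Label |
|---|---|
| SAP 7.6.2.5, opening sentence | not a success (pain at 4 h) |
| SAP 7.6.2.5, success sentence | success (0 at 2, 24, 48 h; none missing) |
| SAP 7.6.2.5, failure sentence | failure (a score above 0) |
| SAP 4.2.1 and protocol 3.2.1 | not a success |
| SAP 7.6.2.4 (2 to 24 h) | failure |

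Only the success sentence gives a different answer.

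**2. How far the overlap extends.** Give each of the seven assessments one of three states (0, pain, missing) and assume no rescue. There are 3^7 = 2,187 patterns.

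- *Success sentence as written.* The scores at 2, 24 and 48 h are fixed at 0. The four scores at 3, 4, 6 and 8 h may be 0 or pain, with at most one missing: 2^4 + 4 × 2^3 = 16 + 32 = 48 patterns.
- *Of these, without any pain.* One pattern with nothing missing plus four with one missing score = 5.
- *Labelled both success and failure.* 48 − 5 = 43.
- *With the wording of 7.6.2.4 and Table 1.* 5 successes, 2,187 − 5 = 2,182 failures, none with both labels and none with neither.

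These are counts of possible patterns, not of subjects. They show that the overlap consists exactly of patterns with pain at 3, 4, 6 or 8 h, and that the parallel wording removes all of it.

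**3. Comparison with the other sustained endpoints.** The SAP defines eight: sustained pain freedom to 24 and 48 h (7.6.2.4 and 7.6.2.5), and sustained pain relief, MBS freedom and normal function, each to 24 and 48 h (Table 1). Seven of the eight success definitions extend the requirement to every non-missing assessment. Only 7.6.2.5 does not.

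**4. Where the three time points probably come from.** Protocol 9.4.4 names 2, 24 and 48 h as the times at which data must be *present*. That is a missing-data rule, and it does not confine the no-pain requirement to those times.

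**5. Size.** The plan states no figure for this endpoint. The effect of a literal reading depends on the share of subjects in each arm with pain at 3 to 8 h, 0 at 2, 24 and 48 h and no rescue. Neither document gives that share.

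For illustration only, use the protocol's power method (two-sided 0.05, Pearson chi-square, n = 600 per arm), with p̄ = (p1 + p2)/2:

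power = Φ{ [ |p2 − p1|√n − 1.96√(2p̄(1 − p̄)) ] / √(p1(1 − p1) + p2(1 − p2)) }

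For 14% against 22% this gives Φ[(1.9596 − 1.0649)/0.5404] = Φ(1.656) = 95.1%, which matches protocol Appendix IV, Table 4. Now *assume* sustained rates and add the same number of misclassified successes to both arms:

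| Assumed placebo / rimegepant | Nothing added | +0.5 points | +3 points |
|---|---|---|---|
| 5% / 12% | 99.2% | 98.9% | 96.8% |
| 7% / 14% | 97.8% | 97.3% | 94.5% |
| 8% / 14% | 91.4% | 90.4% | 85.1% |

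The rates, the additions and their equality across arms are all assumptions, and no Hochberg adjustment is included.

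**The case against.** The strongest reply is that the paragraph already settles the matter. The opening sentence defines the endpoint, the failure sentence excludes any pain, and the sentence between them only says which subjects with one gap are not penalised. To score pain at 4 hours as a success, a programmer would have to disregard both neighbouring sentences and the endpoint definitions in both documents. This stands as far as intent goes: the endpoint is not open to dispute. It does not remove the contradiction, because the middle sentence states its own score condition, the condition is wrong, and no order of precedence is given.

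A reader might infer two stronger things.

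- *That the plan really defines the endpoint at three time points, so early relapses are successes.* The documents do not support this. Taken literally, those subjects are also failures, and every other statement of the endpoint excludes them.
- *That the treatment difference is diluted by an amount that can be estimated.* Protocol 1.3.2 reports phase 2b rates of pain freedom at 2 h and sustained from 2 to 24 h, which imply losses of 1 − 7.4/15.3 = 52% on placebo and 1 − 27.9/31.4 = 11% on 75 mg. These figures stop at 24 h. They do not separate transient pain at 3 to 8 h from pain at 24 h, rescue use or missing data. Any share of the losses treated as transient pain without rescue would be invented. The protocol also permits rescue when pain returns to moderate or severe, and rescue makes the subject a failure anyway. Neither the size nor the direction of an effect can be derived.

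**Conclusion.** The point holds as an internal contradiction in the responder rule of a confirmatory key secondary endpoint. It affects subjects with at most one missing score, 0 at 2, 24 and 48 h, pain at 3, 4, 6 or 8 h and no rescue. The intended label for them is failure. The practical risk is literal programming of the success sentence and the loss of nesting between the two sustained pain freedom endpoints.

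The effect on the result cannot be computed from the documents. That it is probably small is a judgement: the affected group is narrow, and a careful programmer would probably follow the other sentences. The co-primary endpoints and the sample size are not affected. The conclusion rests on the text alone and does not depend on the illustrative power figures.

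**What to change.** Before database lock, reword the success sentence in SAP 7.6.2.5 on the pattern of SAP 7.6.2.4 and the Table 1 rows. Subjects with at most one missing pain score should be successes only if they have a score of 0 "at all other time points including the 2, 24 and 48 hour post-dose time points, will be considered as successes". Leave the failure sentence unchanged, including its rescue rule through 48 hours. Check that the program for this endpoint follows the revised sentence and that every 2 to 48 hour success is also a 2 to 24 hour success.

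The cost is one SAP sentence and one program check. Data collection and the protocol's endpoint definition stay as they are.
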